8.3.2 Pericarditis History

Variable label:	Comment / category labels:
Days since current pericarditis episode was diagnosed prior to IMP start	Take as date of first study treatment dose – date current pericarditis diagnosed. Tabulate as continuous variable.
Symptoms present at time of diagnosis 
 • Pericarditic chest pain • Pericardial rub • New widespread ST-segment elevation or PR segment depression according to ECG findings • Pericardial effusion (new or worsening) 	Tabulate as number of patients with the symptom ticked
CRP level ≥ 1.0 mg/dL within prior 7 days of screening?	Tabulate as categorical variable = Yes./No
Confirmation of Pericarditis diagnosis	Tabulate as categorical variable = CRP level ≥ 1.0 mg/dL within prior 7 days and Pericarditis confirmed by CMR or CRP level ≥ 1.0 mg/dL within prior 7 days only or Pericarditis confirmed by CMR only (CRP < 1.0 mg/dL) Source: reply to inclusion criteria 4.a and 4.b as 'Yes'
Number of previous episodes of pericarditis	Tabulate as categorical variable = 2 episodes,3 episodes,4 episodes or >4 episodes.

8.3.3 Cardiovascular History

Variable label:	Comment / category labels:
History of documented acute myocardial infarction (AMI)?	Tabulate as categorical variable = Yes.
Previous diagnosis of heart failure?	Tabulate as categorical variable = Yes.
History of supraventricular tachycardia	Tabulate as categorical variable = Yes.

Variable label:	Comment / category labels:
History of sustained ventricular arrhythmia?	Tabulate as categorical variable = Yes. Only available for protocol amendment 2
Any other clinically relevant rhythm disorder?	Tabulate as categorical variable = Yes.
Cardiovascular risk factors	
Treated for hypertension	Tabulate as categorical variable = Yes.
Diabetes mellitus	Tabulate as categorical variable = No / Type 1 / Type 2
Treated for hyperlipidemia	Tabulate as categorical variable = Yes.
Diagnosed with chronic kidney disease?	Tabulate as categorical variable = Yes. (Unknown if any is grouped with No)
Lifestyle	
Tobacco use	Tabulate as categorical variable = Never / Former / Current
Alcohol consumption	Tabulate as categorical variable = <1 drink/week / 1 - 7 drinks/week / 8 - 14 drinks/week / >14 drinks/week / Does not want to answer
Cannabinoids consumption	Never / Former / Current
Covid-19 History	
Diagnosed with COVID-19	Tabulate as categorical variable = Yes.
Vaccinated for COVID-19	Tabulate as categorical variable = Yes.

8.3.4 Other medical history

Medical history data will be coded by system organ class and preferred term, using the MedDRA dictionary. Medical history will be summarized by body system. The table will be sorted by alphabetic order, by system organ class, as well as by incidence of preferred term. The N and % will be presented where: N is the number of patients who present at least one occurrence of the medical history and % is the percentage of patients.

8.3.5 Concomitant medications

All medication data will be coded using the WHO Drug dictionary with the primary Anatomical Therapeutic Chemical (ATC) classification selected based on the route and indication.

All medication taken prior to the first dose of IMP intake, i.e with a stop date/time before the date/time of first IMP intake will be classified as prior medications.

For the purpose of classify medication, incomplete medication start and stop date will be imputed as detailed in Section 9.5.2.

Prior, baseline and concomitant medications will be summarized by providing the N and percentage of patients by therapeutic class (ATC second level, e.g. C03: Diuretics) sorted in alphabetical order of the therapeutic class.

All prior, baseline and medications prescribed as of the first IMP intake will be listed by study center, and patient number.

8.3.6 Vital signs

Variable label:	Comment / category labels:
Body height	Tabulate as continuous variable in meters.
Body weight	Tabulate as continuous variable in kg.
Body Mass Index (BMI)	Tabulate as continuous variable in kg/m ² . Estimated as baseline weight in kilograms divided by the squared baseline height in meters.
Systolic blood pressure	Tabulate as continuous variable in mm Hg.
Diastolic blood pressure	Tabulate as continuous variable in mm Hg.
Heart rate	Tabulate as continuous variable in beats/min

8.3.7 Physical examination

Variable label:	Comment / category labels:
Skin	Tabulate as categorical variable = Abnormal (clinically significant).
HEENT	Tabulate as categorical variable = Abnormal (clinically significant).

Variable label:	Comment / category labels:
Chest and respiratory system	Tabulate as categorical variable = Abnormal (clinically significant).
Heart	Tabulate as categorical variable = Abnormal (clinically significant).
Peripheral vascular system	Tabulate as categorical variable = Abnormal (clinically significant).
Abdomen	Tabulate as categorical variable = Abnormal (clinically significant).
Musculo-skeletal system	Tabulate as categorical variable = Abnormal (clinically significant).
Central nervous system	Tabulate as categorical variable = Abnormal (clinically significant).

8.3.8 Questionnaires

Variable label:	Comment / category labels:
NRS	Highest NRS pain score within the past 7 days of Day 1 (documented on the visit 1, page 9) - Tabulate as continuous variable.
C-SSRS – Suicidal Ideation in Lifetime	Count of patients with Yes to any question 1-5 in C-SSRS questionnaire in Lifetime
C-SSRS – Most severe ideation in Lifetime	Tabulate as continuous variable (1-5)
C-SSRS – Suicidal behavior	Count of patients with Yes to any suicidal behavior questions in C-SSRS questionnaire in Lifetime

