### **9.2.10    C-SSRS**

The C-SSRS is a questionnaire designed for the assessment of suicidal ideation and behavior in adolescents and adults.

To monitor for the emergence of suicidal ideation and behavior, patients will undergo C-SSRS evaluations at baseline, at Week 8 and at Week 26.

The questionnaire must be administered by an investigator or other individual that is suitably qualified by education or training. See Appendix 17.4 for a sample C-SSRS - Baseline/Screening version assessment and Appendix 17.5 for a sample post-dose C-SSRS assessment.

If a patient becomes suicidal during the study, an investigator or medically qualified sub-investigator should provide the appropriate treatment to the patient.

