*For reprints of the C-SSRS contact [name]., New York State Psychiatric Institute, [name]; inquiries and training requirements contact [contact]*

© 2008 The Research Foundation for Mental Hygiene, Inc.

## PART 1 OF 5

SUICIDAL IDEATION		Lifetime: Time He/She Felt Most Suicidal	Past _____ Months

Ask questions 1 and 2. If both are negative, proceed to "Suicidal Behavior" section. If the answer to question 2 is "yes", ask questions 3, 4 and 5. If the answer to question 1 and/or 2 is "yes", complete "Intensity of Ideation" section below.
			

1. Wish to be Dead Subject endorses thoughts about a wish to be dead or not alive anymore, or wish to fall asleep and not wake up. Have you wished you were dead or wished you could go to sleep and not wake up?
 
If yes, describe:
		Yes  No 	Yes  No 

2. Non-Specific Active Suicidal Thoughts General non-specific thoughts of wanting to end one's life/commit suicide (e.g., "I've thought about killing myself") without thoughts of ways to kill oneself/associated methods, intent, or plan during the assessment period. Have you actually had any thoughts of killing yourself?
 
If yes, describe:
		Yes  No 	Yes  No 

 Section below not applicable
			

3. Active Suicidal Ideation with Any Methods (Not Plan) without Intent to Act Subject endorses thoughts of suicide and has thought of at least one method during the assessment period. This is different than a specific plan with time, place or method details worked out (e.g., thought of method to kill self but not a specific plan). Includes person who would say, "I thought about taking an overdose but I never made a specific plan as to when, where or how I would actually do it... and I would never go through with it." Have you been thinking about how you might do this?
 
If yes, describe:
		Yes  No 	Yes  No 

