*This scale is intended to be used by individuals who have received training in its administration. The questions contained in the Columbia-Suicide Severity Rating Scale are suggested probes. Ultimately, the determination of the presence of suicidal ideation or behavior depends on the judgment of the individual administering the scale.*

*Definitions of behavioral suicidal events in this scale are based on those used in The Columbia Suicide History Form, developed by [name] and [name], Conte Center for the Neuroscience of Mental Disorders (CCNMD), New York State Psychiatric Institute, [name]. (Oquendo M. A., Halberstam B. & Mann J. J., Risk factors for suicidal behavior: utility and limitations of research instruments. In M.B. First [Ed.] Standardized Evaluation in Clinical Practice, pp. 103 -130, 2003.)*

*For reprints of the C-SSRS contact [name]., New York State Psychiatric Institute, [name]; inquiries and training requirements contact [contact]*

© 2008 The Research Foundation for Mental Hygiene, Inc.

## PART 1 OF 5

SUICIDAL IDEATION		Since Last Visit
Ask questions 1 and 2. If both are negative, proceed to "Suicidal Behavior" section. If the answer to question 2 is "yes", ask questions 3, 4 and 5. If the answer to question 1 and/or 2 is "yes", complete "Intensity of Ideation" section below.		
1. Wish to be Dead Subject endorses thoughts about a wish to be dead or not alive anymore, or wish to fall asleep and not wake up. Have you wished you were dead or wished you could go to sleep and not wake up? If yes, describe:		Yes  No 
2. Non-Specific Active Suicidal Thoughts General non-specific thoughts of wanting to end one's life/commit suicide (e.g., "I've thought about killing myself") without thoughts of ways to kill oneself/associated methods, intent, or plan during the assessment period. Have you actually had any thoughts of killing yourself? If yes, describe:		Yes  No 

 Section below not applicable		

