8.6.3 Change in C-SSRS

The number of patients with C-SSRS ideation and behaviour scores compared to baseline will be summarized.

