Table 29 – Patients with a worsening of C-SSRS ideation and behaviour scores compared to baseline

Table 30 – Laboratory tests results (absolute and change from baseline) during the 26-week study period – Descriptive statistics

Table 31 – Patients who experience changes in laboratory parameters during the 26-week study period

Table 32 – ECG intervals (absolute and change from baseline) during the 26-week study period – Descriptive statistics

Table 33 – Vital signs (absolute and change from baseline) during the 26-week study period – Descriptive statistics

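### The only baseline C-SSRS the SAP derives is lifetime recall, so Table 29 can miss on-treatment ideation or behavior that is no worse than a patient's past

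*SAP*

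**What the plan says.** Change in C-SSRS is a named safety parameter (Protocol 4.2.2; SAP 2.3.4). Protocol 9.2.10 gives the reason for collecting it: "To monitor for the emergence of suicidal ideation and behavior". It is administered at baseline, Week 8 and Week 26.

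The Baseline/Screening form in Protocol Appendix 17.4 has two recall columns. One is headed "Lifetime: Time He/She Felt Most Suicidal". The other covers a recent period, in months for ideation and in years for behavior, with the number left blank on the sample. The post-dose form in Appendix 17.5 has a single column, "Since Last Visit".

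SAP 8.3.8 defines three baseline C-SSRS variables, all on lifetime recall:
- any ideation: "Count of patients with Yes to any question 1-5 in C-SSRS questionnaire in Lifetime";
- severity: "C-SSRS – Most severe ideation in Lifetime", tabulated on 1-5;
- behavior: "Count of patients with Yes to any suicidal behavior questions in C-SSRS questionnaire in Lifetime".

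Nothing is derived from the recent-period column. For follow-up, SAP 8.6.3 says: "The number of patients with C-SSRS ideation and behaviour scores compared to baseline will be summarized". The matching output, Table 29, is titled "Patients with a worsening of C-SSRS ideation and behaviour scores compared to baseline". Neither place names the baseline window or says what counts as worsening.

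**The concern.** The two sides of the comparison cover different spans of time. Baseline is the worst point of a whole life; follow-up is an interval of weeks. A patient with a remote history and no recent ideation who develops ideation on study drug is the kind of case that monitoring for emergence is meant to find. Against a lifetime comparator that patient may show no change, or even an improvement.

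The plan has no clear backstop. SAP 10.3 has no listing of post-dose C-SSRS results, and no table counts post-dose ideation or behavior irrespective of baseline. A reassuring Table 29 could therefore mean either that nothing emerged or that what emerged did not exceed the patient's past.

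**Working it through.** The plan states no figure to reproduce. The check is to apply the comparison with the only baseline the SAP defines and see which cases it can detect.

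**Inputs.** Lifetime worst ideation L, 1 to 5 (SAP 8.3.8). On-treatment ideation F, 1 to 5, from the post-dose form (Appendix 17.5). Recent-period ideation R, from the second column of the baseline form (Appendix 17.4), not used by the SAP.

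**Assumed rule.** The SAP gives none, so I take worsening to be F > L on the severity score, or a move from No to Yes on a yes/no item.

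**Severity score.** For patients with a past history and some ideation on treatment, there are 5 × 5 = 25 possible pairs.

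| Lifetime worst L | Flagged (F > L) | Not flagged (F ≤ L) |
|---|---|---|
| 1 | 4 | 1 |
| 2 | 3 | 2 |
| 3 | 2 | 3 |
| 4 | 1 | 4 |
| 5 | 0 | 5 |
| Total | 10 | 15 |

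These are counts of possible combinations. They say nothing about how often each occurs.

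**Yes/no items.** Lifetime Yes followed by on-treatment Yes is not a move from No to Yes, so 0 of the 25 pairs are flagged on the ideation item. The same holds for behavior in a patient with past behavior. First-ever behavior in a patient with past ideation only is still flagged.

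**Example.** Take L = 4 many years ago, R = 0, and F = 3 or 4 at Week 8. Against lifetime the change is 3 − 4 = −1 or 4 − 4 = 0, so no worsening. Against the recent period it is 3 − 0 = +3 or 4 − 0 = +4, so emergent.

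**With the recent period as comparator.** When R = 0, every F from 1 to 5 exceeds it, so all 25 of 25 pairs are flagged.

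**Patients with no history.** Severity runs 1-5 with no zero, and SAP 9.2 leaves missing values missing, so these patients have no baseline severity to subtract. The separate yes/no item still shows No to Yes. This is a smaller, related gap.

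**The case against.** The strongest objection is that the link from SAP 8.3.8 to Table 29 is inferred. Section 8.3 describes baseline characteristics; it does not say its variables serve as comparators for safety change. Its general definition of a baseline variable, data obtained before the start of study drug, would also admit the recent-period column. This stands: no written rule tells the programmer to use lifetime. But the lifetime variables are the only baseline C-SSRS variables the SAP derives, and if they are not the comparator, then the comparator is undefined.

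A reader might infer that Table 29 is blind in everyone with a past history. It is not. Severity above the lifetime worst is flagged (10 of 25 pairs), as is first-ever behavior. The miss is complete only for same-kind yes/no items and for lifetime severity 5.

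A reader might also want a number of patients. Assuming 5% to 30% have a lifetime history gives 0.05 × 25 = 1.25 to 0.30 × 25 = 7.5 of about 25. The documents support no such prevalence. The product counts patients with a history, not missed events. Exclusion 15 bars suicidal tendency on the C-SSRS at screening without saying whether lifetime history counts, so the number could be near zero.

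Emergent suicidality could also appear in the adverse event tables and Listing 5, since Protocol 9.2.11.1 defines adverse events broadly. That helps only in part: no passage requires a positive C-SSRS to be reported as an adverse event, and the same section tells sites not to question patients about specific events.

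Finally, this is a descriptive single-arm pilot, so no test is affected. That limits the consequence to how one safety table reads, but C-SSRS change is a named safety parameter.

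**Conclusion.** The point holds as a conditional one. If Table 29 uses the only baseline C-SSRS variables the SAP defines, it can miss on-treatment ideation or behavior in a patient whose past level was as high or higher: always for same-kind yes/no items, and on severity whenever the on-treatment level does not exceed the lifetime worst. If some other comparator is intended, the SAP does not say which, and 8.6.3 still needs completing.

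The conclusion rests on two assumptions: that the lifetime variables are the comparator, and that worsening means a higher category or a change from No to Yes. The number of patients affected cannot be estimated from the documents. The change is worth making because the table is meant to detect emergence and the main remedy uses data already planned for collection.

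**What to change.** In SAP 8.6.3 and Table 29:

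1. Count and list every patient with any post-dose ideation (categories 1-5) or any post-dose behavior, at Week 8 or Week 26, regardless of history. This needs no baseline and no new data.
2. For ideation, define worsening as a post-dose category above the recent-months baseline, with no ideation coded 0, wherever that column was captured. State the recall period actually used. It is blank on the sample form and cannot be set retrospectively for patients already assessed; SAP section 4 records 6 enrolled under amendment 1. Where the column was not captured, rely on item 1.
3. For behavior, rely on item 1, because the second column is in years and is a poor recent window.
4. Keep the lifetime variables in 8.3.8 as descriptive baseline characteristics only.

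The cost is SAP wording, a revised Table 29 shell and one short listing. The downside is slightly more table work and a count that may look less favorable.

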8.3.9 Standard 12-lead Electrocardiogram (ECG)

Variable label:	Comment / category labels:
Ventricular rate	Tabulate as continuous variable in beats/min.
RR interval	Tabulate as continuous variable in milliseconds.
PR interval	Tabulate as continuous variable in milliseconds.
QRS interval	Tabulate as continuous variable in milliseconds.
QT interval	Tabulate as continuous variable in milliseconds.
QTc interval (Fridericia's formula)	Tabulate as continuous variable in milliseconds.

Variable label:	Comment / category labels:
Patients with abnormal ECG	Tabulate as categorical value = Yes. A Listing of ECG abnormalities considered clinically significant will be provided I

8.3.10 Laboratory tests

The date and time when the laboratory tests were performed in addition to the laboratory test results as entered in eSOC DAT will be used. A baseline laboratory sample is defined as a blood sample where the blood draw date / time is < the start of IMP. All available, baseline laboratory test results will be presented for:

8.3.10.1 *Chemistry*:

Creatinine, eGFR, Total bilirubin, Aspartate-Amino-Transferase (AST), Alanine Transaminase (ALT), Alkaline phosphatase, CRP.

The e-GFR will be calculated using the abbreviated CKD-EPI Creatinine Equation (2021) formula:

If $Scr \geq k$: $eGFR (\text{mL/min}/1.73\text{m}^2) = 142 \times (Scr/k)^{-1.2} \times 0.9938^{\text{Age}} \times 1.012$ [if female]

Else: $eGFR (\text{mL/min}/1.73\text{m}^2) = 142 \times (Scr/k)^{\alpha} \times 0.9938^{\text{Age}} \times 1.012$ [if female]

where:

Scr = serum creatinine in mg/dL

k = 0.7 (females) or 0.9 (males)

Age (years)

α = -0.241 (female) or -0.302 (male)

8.3.10.2 *Hematology*:

Red Blood Cell Count, Hemoglobin, Hematocrit, Platelets count, White Blood Cell count (WBC), Monocytes, Lymphocytes, Neutrophils, Eosinophils, Basophils and International Normalized Ratio (INR)

The laboratory test results will be converted into SI units as displayed in Table 8-1

Table 8-1: SI units to be used

Assay	SI unit
Creatinine	mg/dL
eGFR	mL/min/1.73m ²
Total bilirubin	mg/dL
Aspartate-Amino-Transferase (AST)	U/L
Alanine Transaminase (ALT)	U/L
Alkaline phosphatase	U/L
C-Reactive Protein (CRP)	mg/dL
Red Blood Cell Count	10 ⁶ /µL
Hemoglobin	g/dL
Hematocrit	%
Platelets count	10 ³ /µL
White Blood Cell count (WBC)	10 ³ /µL
Monocytes	10 ³ /µL
Lymphocytes	10 ³ /µL
Neutrophils,	10 ³ /µL
Eosinophils	10 ³ /µL
Basophils	10 ³ /µL
International Normalized Ratio (INR)	No unit

The local laboratory normal ranges will be used to identify assays for which the results are either within, above or below the local normal range.

Assays reported as ‘<XXX’ will be imputed to 0 (e.g. CRP <0.3 mg/dL → value imputed as 0 mg/dL).

For all assays, the results will be tabulated as follows:

- Standard descriptive statistics for continuous variables.
- Standard descriptive statistics for categorical variables for values that are below the lower limit of normal / within normal range / above the upper limit of normal.
- For all baseline laboratory test data which are gender dependent – i.e. Alkaline phosphatase, ALT, AST, Basophils, creatinine, Eosinophils, Lymphocytes, Monocytes, Neutrophils, Platelets count, INR, HGB, HCT, RBC and WBC – standard descriptive statistics for continuous variables will be tabulated separately for men and women.

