#### 4.1.3 Additional Efficacy Parameters of Interest

- Pain score using 11-point NRS from baseline (highest pain score within the past 7 days of Day 1) to Week 26 (highest pain score during the past 7 days of Week 26)
- Percentage of patients with normalized CRP levels at 8 weeks (for patients with CRP  $\geq 1.0$  mg/dL at baseline)
- Percentage of patients with pericarditis recurrence during the EP
- Percentage of patients with normalized CRP levels at 26 weeks (for patients with CRP  $\geq 1.0$  mg/dL at baseline)
- Time to CRP normalization for patients with CRP  $\geq 1.0$  mg/dL at baseline
- CRP change from baseline at 26 weeks (%)

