4.1 Inclusion Criteria

Per protocol amendment 2, the following inclusion criteria had to be met to be eligible for enrolment:

1. Male or female 18 years of age or older
2. Diagnosis of at least two episodes of recurrent pericarditis
3. At least 1 day with pericarditis pain ≥ 4 on the 11-point NRS within prior 7 days
4. One of
 - a. CRP level ≥ 1.0 mg/dL within prior 7 days OR
 - b. Evidence of pericardial inflammation assessed by delayed pericardial hyperenhancement on cardiac magnetic resonance imaging (CMR)
5. Currently receiving non-steroidal anti-inflammatory drugs (NSAIDs) and/or colchicine and/or corticosteroids for treatment of pericarditis (in any combination) in stable doses

6. Male patients with partners of childbearing potential who have had a vasectomy or are willing to use double barrier contraception methods during the conduct of the study and for 2 months after the last dose of study drug.
7. Women of childbearing potential willing to use an acceptable method of contraception starting with study drug administration and for a minimum of 2 months after study completion. Otherwise, women must be postmenopausal (at least 1 year absence of vaginal bleeding or spotting and confirmed by follicle stimulating hormone [FSH] ≥ 40 mIU/mL [or ≥ 40 IU/L] if less than 2 years postmenopausal) or be surgically sterile.

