8.3 Description of Demographic and Baseline characteristics

A baseline variable is defined as data obtained / collected prior to or on the same day as enrollment but prior to the start of the IMP. Baseline characteristics / demographics will be summarized as either continuous or categorical variables (as appropriate) as described in section 9.1. Baseline information will be summarized for the FAS dataset only.

All demographic and baseline characteristics will be listed by study center, and patient number.

If two baseline values are available for any given variable, the closest value obtained prior to the start of the IMP will be presented as the baseline value. The baseline variables which will be tabulated are shown in the following tables:

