8.5.2 Additional efficacy analysis

- The change in patient-reported pericarditis pain using an 11-point NRS from baseline to 26 weeks will be summarized as a continuous variable.
- The change in patient-reported pericarditis pain using an 11-point NRS from baseline to other intermediate weeks (i.e. visits 3,4,5,6,7) will be summarized as a continuous variable.
- Patients with normalized CRP levels (i.e with a CRP \leq 0.5 mg/dL) at 8 weeks (for patients with CRP \geq 1.0 mg/dL at baseline) will be summarized as a categorical variable
- Patients with normalized CRP levels (i.e with a CRP \leq 0.5 mg/dL) at 26 weeks (for patients with CRP \geq 1.0 mg/dL at baseline) will be summarized as a categorical variable
- Patients with pericarditis recurrence during the extension period (EP), i.e with an adverse event occurring between week 8 and week 26 and coded with the following LLT code 10087207 (Recurrent pericarditis) will be summarized as a categorical variable

- Time to CRP normalization (in days) (i.e time between IMP start date up to the first blood draw date when $CRP \leq 0.5 \text{ mg/dL}$) for patients with $CRP \geq 1.0 \text{ mg/dL}$ at baseline will be summarized as a continuous variable. If CRP had not normalized at the timepoint assessed (i.e 8 week visit date (for SSA) or 26 weeks visit date for the final analysis), the patients concerned will not be included in the analysis for this outcome.
- CRP change from baseline at 26 weeks (%) will be summarized as a continuous variable.

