8.6.4 Laboratory parameters

Descriptive statistics of absolute value and change from baseline for laboratory values, including liver function parameters and INR, will be presented by follow-up time points.

The number and percentage of patients with changes in laboratory test results during the course of the study, i.e. change from normal to high or low, based on the local reference ranges will be summarized by assay concerned.

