9.2 Handling of missing data

Missing data will be treated as missing, not imputed, unless otherwise stated.

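### Setting CRP results reported as `<x` to 0 (SAP 8.3.10) does not suit the Week 26 percent CRP change: a `<x` baseline leaves it undefined, and, if the rule also covers follow-up, a `<x` follow-up is recorded as exactly −100%

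*SAP*

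**What the plan says.** The substitution rule is in SAP 8.3.10: results given as below a reporting limit "will be imputed to 0 (e.g. CRP <0.3 mg/dL" is the SAP's own example). The rule names no visit. It stands under SAP 8.3, headed "Description of Demographic and Baseline characteristics".

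The affected endpoint is in Protocol 4.1.3 ("CRP change from baseline at 26 weeks", expressed in percent) and in SAP 8.5.2: "CRP change from baseline at 26 weeks (%) will be summarized as a continuous variable". The CRP normalization and time-to-normalization endpoints in the same lists are limited to baseline CRP of at least 1.0 mg/dL. The percent change is not, and neither is its output, Table 20.

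Low baselines are expected. SAP 4.1 accepts, as an alternative to raised CRP, "Evidence of pericardial inflammation assessed by delayed pericardial hyperenhancement on cardiac magnetic resonance imaging (CMR"), and SAP 8.3.2 tabulates a category "Pericarditis confirmed by CMR only (CRP < 1.0 mg/dL").

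For follow-up, SAP 8.6.4 plans "Descriptive statistics of absolute value and change from baseline for laboratory values" by time point (Table 30) and gives no rule for `<x` results. SAP 9.2 says: "Missing data will be treated as missing, not imputed, unless otherwise stated". SAP 9.1 reports counts, means, SDs, medians, interquartile ranges and extremes.

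**The concern.** A percent change needs a positive denominator, and it is sensitive to the value given to a result known only to lie below a limit. Zero fails at baseline and is the extreme choice at follow-up.

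At baseline, the patient has no percent change at all, and the SAP does not say what then happens. Under SAP 9.1 and 9.2 the value would most likely be treated as missing and show only as a smaller N in Table 20. Such a patient can show only no measurable change or a rise, so the loss is not neutral in a period when background therapy is being weaned.

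At follow-up, if the rule applies there, 0 is the most favourable value possible, so the error always runs towards benefit. The study is uncontrolled and purely descriptive, so the summary figures are themselves the result.

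**Working it through.** **Inputs.** Example limit x = 0.3 mg/dL (SAP 8.3.10); entry threshold 1.0 mg/dL (SAP 4.1); normalization threshold 0.5 mg/dL (SAP 8.5.2); about 25 patients (Protocol 11.1). The SAP writes no formula for percent change, so I use the usual one, 100 × (follow-up − baseline) / baseline. There is no planned figure to reproduce. Local reporting limits, the share of `<x` results, the share entering on MRI alone and the number of Week 26 values are not given. Baselines of 2.0 and 5.0, and the shares and counts below, are assumptions chosen to show a range.

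**1. `<x` at baseline.** The baseline becomes 0, so the formula divides by 0 and is undefined whatever the follow-up value. Patients who do not enter the extension finish at Week 8 (Protocol 6.3), so Week 26 values may be fewer than 25. One lost patient is 1/25 = 4%, 1/20 = 5% or 1/15 = 6.7%; two are 8%, 10% or 13%.

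**2. `<x` at follow-up, if the rule applies there.** With baseline b > 0, the recorded change is 100 × (0 − b)/b = −100%, whatever b or x is. The true change lies between −100% and 100 × (x − b)/b, so the fall is overstated by up to 100 × x/b points:

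| Baseline b (mg/dL) | Recorded with 0 | Largest overstatement, 100 × 0.3/b | Recorded with x/2 = 0.15 | Recorded with x = 0.3 |
|---|---|---|---|---|
| 1.0 | −100% | 30 points | −85% | −70% |
| 2.0 | −100% | 15 points | −92.5% | −85% |
| 5.0 | −100% | 6 points | −97% | −94% |

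With x/2 the largest error is halved (15, 7.5 and 3 points) and can go either way.

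**3. Effect on the mean.** If a share f of Week 26 values is `<x` and all baselines equal b, the mean fall is overstated by at most f × 100 × x/b. For f = 10%, 25% and 50% this is 3, 7.5 and 15 points at b = 1.0, and 0.6, 1.5 and 3 points at b = 5.0. If at least half of the evaluable patients have a `<x` follow-up, the median is exactly −100%.

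**4. Substitution does not rescue the denominator.** Take a baseline of `<0.3` rising to 0.6. With x/2 the change is 100 × (0.6 − 0.15)/0.15 = +300%; with x it is 100 × (0.6 − 0.3)/0.3 = +100%. For illustration, 24 patients at −80% and one at +300% give a mean of (24 × −80 + 300)/25 = −64.8%. One invented denominator has moved the mean by 15.2 points.

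**5. Other CRP outputs.** Absolute change is off by less than x. A result of `<0.3`, set to 0 or not, is at or below 0.5 and is correctly counted as normalized; the same holds for any limit up to 0.5.

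**The case against.** The strongest objection is that the text does not establish the follow-up problem. SAP 8.3 is the baseline section, and 8.3.10 speaks of baseline results. A reader might infer that the SAP builds a bias towards benefit into the Week 26 CRP result. The documents do not support that as a definite statement. General wording, and a section that also holds the unit conversions and local normal ranges, make the wider reading plausible, but no sentence confirms it. If the rule is for baseline only, the −100% effect falls away, and what remains is that no follow-up rule is stated.

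Second, leaving a patient with no measurable CRP out of a percent-reduction summary is defensible. I agree, provided the exclusion is stated and counted. Nor is such a patient lost to the CRP analysis: the absolute change in Table 30 still includes the patient.

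Third, SAP section 7 already summarizes CRP and its change for patients with baseline CRP of at least 1 mg/dL. This shows that the subset is in use, but it belongs to the Week 8 staged analysis and gives no percent, so it does not settle Week 26.

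Finally, using x/2 throughout could do harm. Step 4 bears this out, so substitution should not extend to the denominator of the unrestricted percent change.

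**Conclusion.** The point holds as a minor one. It is certain that a `<x` baseline makes the Week 26 percent change undefined, that entry on MRI alone makes such a baseline possible, and that no sentence deals with it. It is conditional on the rule covering follow-up that each positive baseline followed by `<x` is recorded as −100%, overstating the fall by up to 30 points at baseline 1.0 and 6 at 5.0 with x = 0.3.

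How many patients this touches cannot be told from the documents; it may be none. The worst-case means in step 3 put every baseline at the stated value and every `<x` result just under the limit. A reader should not extend the point to the primary pain endpoint, which does not use CRP, or to CRP normalization, which is classified correctly at the SAP's example limit.

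**What to change.** In the SAP:

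- State that the rule for `<x` results applies at all visits.
- For CRP follow-up values, replace 0 with x/2, and use x as a sensitivity analysis.
- Beside the unrestricted protocol endpoint, report percent CRP change at Week 26 for patients with baseline CRP of at least 1.0 mg/dL.
- In the unrestricted endpoint, do not use a substituted value as denominator. Count patients with a `<x` baseline as not evaluable for percent change, give their number and show their absolute change. For that absolute change use the same substitute at both visits; otherwise `<0.3` followed by `<0.3` would appear as a rise of 0.15 − 0 = 0.15 mg/dL.
- Report the number of `<x` CRP results at baseline and at Week 26.

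The cost is a few SAP lines and a few lines of code. No protocol change is needed, because the unrestricted endpoint stays. The downsides are that the reported percent reduction may be somewhat smaller, and that patients with a `<x` baseline remain outside the percent summary.
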